- b. The Week 8 study visits apply to all subjects whose treatment duration is 12 weeks and 16 weeks in accordance with Section 5.1. The Week 12 study visits apply to all subjects whose treatment duration is 16 weeks in accordance with Section 5.1. Subjects who prematurely discontinue the Treatment Period should return to the site to complete the Premature D/C Visit Procedures (preferably prior to the initiation of any other anti-HCV therapy).
- c. Parent(s)/guardian(s) need to sign an IRB/IEC approved informed consent for the study prior to performing any screening or study-specific procedures. Additionally an assent from the subject will be obtained to meet the institution's IEC requirements, as applicable.
- d. A complete medical history will be taken at Screening and will be updated at the Study Day 1 Visit prior to study drug administration and will serve as the Baseline for clinical assessment.
- e. A symptom-directed physical examination may be performed at any other visit, when necessary.
- f. ECG will be measured only in the intensive PK portion of both parts, prior to any blood collection procedures, excluding subjects in Japan.
- g. A positive urine pregnancy test requires a confirmatory serum test. (Refer to Section 5.3.1.1 [Pregnancy Test] for additional details.) Females who are experiencing menses or are nearing sexual maturation in the opinion of the PI or who are of childbearing potential should have urine pregnancy testing done through Post-Treatment Week 4. Females of non-childbearing potential (as defined per protocol Inclusion Criteria 3) at Screening do not require pregnancy testing.

- h. For non-cirrhotic subjects: Coagulation panel performed only at Day 1, at EOT/premature D/C, and as clinically indicated.  
For cirrhotic subjects: Coagulation panel is required at all treatment visits, including the EOT/premature D/C visit.
- i. FSH for all female subjects aged 9 to < 18 years old.
- j. Subjects with no history of cirrhosis who have not had a liver biopsy within 24 months prior to screening, or Fibroscan within 6 months prior to screening will have a screening FibroTest and APRI to determine the presence or absence of cirrhosis for the purpose of treatment assignment. Subjects who have a liver biopsy or FibroScan indicating cirrhosis at any time in the past will not need a Fibrotest and APRI to be performed at screening as evidence of cirrhosis.

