6.2 Definition of Analysis Windows

For efficacy analyses of HCV RNA and resistance, the time windows specified in [Table 3](#) and [Table 4](#) describe how HCV RNA and resistance data are assigned to protocol-specified time points during the Treatment and PT Periods, respectively. All time points and corresponding time windows are defined based on the date/time of blood sample collection.

For safety laboratory data, vital signs, and growth and development endpoints (except growth rate), the time windows specified in [Table 3](#) and [Table 5](#) describes how data are assigned to protocol specified time points. For the calculation of growth rate only, the time window specified in [Table 6](#) will be used to assign height to a specific visit window before growth rate will be calculated as the change in height over change in age from the previous visit at Post-Treatment Weeks 12, 48, 96, and 144.

For PRO questionnaire, the time windows specified in [Table 7](#) and [Table 8](#) describes how data are assigned to protocol specified time points.

For palatability questionnaire, the time windows specified in [Table 9](#) describes how data are assigned to protocol specified time points during the treatment period.

For longitudinal Fibrotest and APRI, the time windows specified in [Table 10](#) describes how data are assigned to protocol specified time points during the Post-Treatment period.

If more than one assessment is included in a time window, the assessment closest (except in analyses of SVR) to the nominal time will be used. If there are two observations equally distant to the nominal time, the latest one will be used in analyses. For analyses of SVR (e.g., SVR₁₂), the last value in the window will be used.

If multiple measurements are made on the same day for a safety laboratory parameter, a vital sign parameter, or a growth and development endpoint, the average of the values will be used to calculate descriptive statistics and in analyses of the mean change from baseline.

Table 3. Analysis Time Windows for HCV RNA, Resistance Endpoints, Laboratory, Vital Sign Measurements, Growth and Development Endpoints (Treatment Period)

Scheduled Visit	Nominal Day (Study Day)	Time Window (Study Day Range)
Day 1/Baseline ^a	1	≤ 1 ^a
Week 2	14	2 to 21
Week 4	28	22 to 42
Week 8	56	43 to 70
Week 12 ^b	84	71 to 98
Week 16 ^c	112	99 to 126
Final Treatment Visit ^d	2 to ≤ 2 days after last dose of study drug	

a. Day of first dose of study drug.

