b. For 12-week treatment only.

c. For 16-week treatment only.

d. The last value within the window will be used to define the Final Treatment Visit value. The upper bound of this Final window is Study Drug End Day ≤ 2.

Note: Data must also have Study Drug End Day ≤ 2 for all windows. The result closest to the scheduled time point will be used.

Table 4. Analysis Time Windows for HCV RNA and Resistance Endpoints (Post-Treatment Period)

Scheduled Visit ^a	Nominal Day (Study Drug End Day)	Time Window (Study Drug End Day Range)
Post-Treatment Week 4	28	3 to 56
Post-Treatment Week 12	84	57 to 126
Post-Treatment Week 24	168	127 to 210
Post-Treatment Week 36	252	211 to 294
Post-Treatment Week 48	336	295 to 504
Post-Treatment Week 96	672	505 to 840
Post-Treatment Week 144	1,008	841 to 1,999
SVR ₄ ^b	28	3 to 56
SVR ₁₂ ^b	84	57 to 126
SVR ₂₄ ^b	168	127 to 210

a. Post-Treatment Visits are applicable to subjects who received at least one dose of study drug.

b. For SVR windows, the last value in the window will be used.

Note: The result closest to the scheduled time point will be used, except for SVR₄, SVR₁₂, and SVR₂₄. Data must also have Study Drug End Day > 2 for all windows. Study Drug End Day 0 is defined as the day of the last dose of study drug.

Table 5. Laboratory Data, Vital Sign Measurements, Growth and Development Endpoints (Except Growth Rate) Visit Windows (Post-Treatment Period)

Scheduled Time	Nominal Day (Study Drug End Day)	Time Window (Study Drug End Days Range)
Post-Treatment Week 4	28	3 to 42
Post-Treatment Week 12	84	71 to 126
Post-Treatment Week 24	168	127 to 210
Post-Treatment Week 36	252	211 to 294
Post-Treatment Week 48	336	295 to 504
Post-Treatment Week 96	672	505 to 840
Post-Treatment Week 144	1,008	841 to 1,999
Final Post-Treatment Visit ^a	> 2 days after the last dose of study drug	

a. The last value within the Post-Treatment Period window will be used to define the final post-treatment value. The lower bound of this Final window is Study Drug End Day 3.

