10.7 Additional Efficacy Analyses

The following additional efficacy endpoints will be summarized and analyzed for the ITT population:

- The percentage of subjects with HCV RNA $< \text{LLOQ}$ at each post-baseline visit in the Treatment Period (using data as observed) by age group and overall;
- The percentage of subjects with SVR₁₂ by age group;
- The percentage of subjects with SVR₄ by age group and overall;

- The percentage of subjects with SVR₂₄ by age group and overall;

All rates will be presented with two-sided 95% confidence intervals using the Wilson's score method.

A summary of the subjects who completed treatment and relapsed (defined as **Relapse_{overall}**) will be prepared displaying the number of subjects relapsing overall and by SVR visit window (within the SVR₄, SVR₁₂, SVR₂₄ windows or after SVR₂₄ window), including the subject number and the SVR visit window corresponding to the first HCV RNA value of those indicating the occurrence of relapse. A similar listing will be prepared for subjects who prematurely discontinued treatment and relapsed after having HCV RNA < LLOQ at their Final Treatment Visit. A listing of subjects in the ITT population excluded from the relapse denominator (e.g., study drug duration < 52 days for subjects assigned to 8 weeks of treatment) will be provided, as applicable.

The number and percentage of subjects who do not achieve SVR₂₄ will be summarized by reason for non-response (as defined in Section 10.1). A listing of subject numbers and reason for non-response will be prepared.

The concordance between SVR₁₂ and SVR₂₄ will be assessed by the agreement between SVR₁₂ and SVR₂₄ and the positive predictive value (PPV) and negative predictive value (NPV) of SVR₁₂ on SVR₂₄. The agreement between SVR₁₂ and SVR₂₄ is a percentage defined as the number of subjects achieving both SVR₁₂ and SVR₂₄ and the number of subjects where both SVR₁₂ and SVR₂₄ are not achieved. The PPV of SVR₁₂ on SVR₂₄ is the proportion of subjects who achieve SVR₂₄ out of all subjects who achieved SVR₁₂. The NPV of SVR₁₂ on SVR₂₄ is the proportion of subjects who do not achieve SVR₂₄ out of all subjects who did not achieve SVR₁₂. Similarly, the concordance between SVR₄ and SVR₁₂ will be summarized.

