11.3.2 Statistical Methods

The baseline value for clinical laboratory tests will be the last non-missing measurement on or before the day of the first dose of study drug. Values on Day 1 must also be before the time of first dose if time is available. The same baseline value will be used for change to Treatment Period visits and change to Post-Treatment Period visits.

Mean changes from baseline to each post-baseline visit, including applicable post treatment visits, will be summarized for each age group and overall. Each protocol-specified laboratory parameter will be summarized with the sample size, baseline mean, visit mean, change from baseline mean, standard deviation, minimum, median, and maximum.

The laboratory parameters defined in [Table 15](#) will be assigned a toxicity grade of 1, 2, 3, or 4. The number and percentage of subjects with a maximum toxicity grade of 1, 2, 3 or 4 will be summarized for each age group and overall. To be counted, the post-baseline value must have a toxicity grade that is more extreme than the toxicity grade corresponding to the baseline value. The summary will also include the number and percentage of subjects with a maximum of at least Grade 3 for all laboratory parameters in

Table 15. A listing of all relevant laboratory parameters will be provided for each subject who had an increase to Grade 2 or higher for all laboratory variables in Table 15.

Table 15. Definitions of Toxicity Grades 1, 2, 3, and 4 for Laboratory Values

Test	Grade 1	Grade 2	Grade 3	Grade 4
ALT	> ULN – 3 × ULN	> 3 – 5 × ULN	> 5 – 20 × ULN	> 20 × ULN
AST	> ULN – 3 × ULN	> 3 – 5 × ULN	> 5 – 20 × ULN	> 20 × ULN
Alkaline Phosphatase	> ULN – 2.5 × ULN	> 2.5 – 5 × ULN	> 5 – 20 × ULN	> 20 × ULN
GGT	> ULN – 2.5 × ULN	> 2.5 – 5 × ULN	> 5 – 20 × ULN	> 20 × ULN
Total Bilirubin	> ULN – 1.5 × ULN	> 1.5 – 3 × ULN	> 3 – 10 × ULN	> 10 × ULN
Hemoglobin	< LLN – 100 g/L	< 100 – 80 g/L	< 80 g/L	--
White blood cells	< LLN – 3.0 × 10 ⁹ /L	< 3.0 – 2.0 × 10 ⁹ /L	< 2.0 – 1.0 × 10 ⁹ /L	< 1.0 × 10 ⁹ /L
Absolute Neutrophil Count	< LLN – 1.5 × 10 ⁹ /L	< 1.5 – 1.0 × 10 ⁹ /L	< 1.0 – 0.5 × 10 ⁹ /L	< 0.5 × 10 ⁹ /L
Platelet count	< LLN – 75.0 × 10 ⁹ /L	< 75.0 – 50.0 × 10 ⁹ /L	< 50.0 – 25.0 × 10 ⁹ /L	< 25.0 × 10 ⁹ /L
INR	> 1 – 1.5 × ULN	> 1.5 – 2.5 × ULN	> 2.5 × ULN	--
Glucose (increased)	> ULN – 8.9 mmol/L	> 8.9 – 13.9 mmol/L	> 13.9 – 27.8 mmol/L	> 27.8 mmol/L
Glucose (decreased)	< LLN – 3.0 mmol/L	< 3.0 – 2.2 mmol/L	< 2.2 – 1.7 mmol/L	< 1.7 mmol/L

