11.4.2 Statistical Methods

The baseline value for vital signs will be the last measurement on or before the day of the first dose of study drug. The same baseline value will be used for change to Treatment Period visits and change to Post-Treatment Period visits.

Changes from baseline to each post-baseline visit, including applicable post-treatment visits, will be summarized for each age group and overall. Each vital sign parameter will be summarized with the baseline mean, visit mean, change from baseline mean, standard deviation, minimum, median, and maximum.

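### SAP Table 3 closes the Week 12 window to 16-week subjects, so the descriptive Week 12 summaries omit a visit that the protocol schedules for them

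*SAP*

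**What the plan says.** SAP Section 6.2, Table 3 is titled "Analysis Time Windows for HCV RNA, Resistance Endpoints, Laboratory, Vital Sign Measurements, Growth and Development Endpoints (Treatment Period)". Its Week 12 row covers Study Days 71 to 98 (nominal Day 84) and carries footnote b, "For 12-week treatment only". The Week 16 row covers Days 99 to 126 and carries footnote c, "For 16-week treatment only". The Week 8 row, Days 43 to 70, has no such restriction. The table also defines a Final Treatment Visit, which runs from Study Day 2 to two days after the last dose: "The last value within the window will be used to define the Final Treatment Visit value".

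Protocol Appendix C, Treatment Period, note b states: "The Week 12 study visits apply to all subjects whose treatment duration is 16 weeks in accordance with Section 5.1". The Week 12 column of that schedule includes HCV RNA, hematology and chemistry, vital signs, weight and height. Subjects on 12 weeks have their end-of-treatment visit at Week 12 and follow the end-of-treatment column instead.

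Three SAP sections call for summaries by visit:

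- Section 10.7 reports the percentage with HCV RNA below LLOQ "at each post-baseline visit in the Treatment Period (using data as observed) by age group and overall".
- Section 11.3.2, for laboratory data: "Mean changes from baseline to each post-baseline visit, including applicable post treatment visits, will be summarized for each age group and overall".
- Section 11.4.2, for vital signs: "Changes from baseline to each post-baseline visit, including applicable post-treatment visits, will be summarized for each age group and overall".

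Section 10.9 adds weight, height and BMI z scores at each applicable post-baseline visit.

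**The concern.** The SAP shuts out of its Week 12 window the very group for which the protocol's Week 12 column exists. A programmer who follows Table 3 to the letter would leave these subjects' Week 12 values out of every Week 12 row, although the samples and measurements were taken.

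The restriction does not look like a deliberate choice. Table 3 is not confined to end-of-treatment data: Week 8 is open to all regimens, so 12-week and 16-week subjects keep their interim Week 8 values. The same reasoning would let 16-week subjects keep Week 12. The footnote does suit Tables 7 and 9. During treatment, PedsQL is collected only at Day 1 and end of treatment, and palatability only at Week 2 and at end of treatment or discontinuation. Carry-over of the wording between tables is a plausible explanation, but the documents do not establish it. SAP Section 12.1, which lists departures from the protocol, does not mention dropping this visit.

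At stake is the completeness of some descriptive tables, and agreement between the two documents on which visits are analysed.

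**Working it through.** No figure in the plan is in dispute. The check is to place each scheduled on-treatment visit in the Table 3 windows, first with the footnotes taken literally and then with footnote b widened.

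Inputs: the window limits and footnotes b and c of SAP Table 3, and the scheduled post-baseline treatment visits of Protocol Appendix C at their nominal days (14, 28, 56, 84, 112).

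| Nominal day | Window containing it | 8-week subject | 12-week subject | 16-week subject, literal | 16-week subject, footnote b widened |
|---|---|---|---|---|---|
| 14 | 2 to 21 | Week 2 | Week 2 | Week 2 | Week 2 |
| 28 | 22 to 42 | Week 4 | Week 4 | Week 4 | Week 4 |
| 56 | 43 to 70 | Week 8 | Week 8 | Week 8 | Week 8 |
| 84 | 71 to 98 | not scheduled | Week 12 | **none** | Week 12 |
| 112 | 99 to 126 | not scheduled | not scheduled | Week 16 | Week 16 |

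- Length of the gap for 16-week subjects: 98 − 71 + 1 = 28 days.
- Share of their scheduled post-baseline treatment visits without a window: 1 of 5, or 20%.
- Widening footnote b closes the gap and changes no assignment for 8-week or 12-week subjects.

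**Does another rule catch the value?** The Final Treatment Visit range spans Day 84 but takes only the last value. A 16-week subject who stops early, with Week 12 as the last on-treatment measurement, keeps it there. A subject with a later on-treatment value does not, and the Week 12 value then enters no visit summary. No other SAP text gives Days 71 to 98 of a 16-week subject a scheduled visit.

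**Which outputs depend on the Week 12 window?**

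- Dependent: the by-visit summaries of HCV RNA below LLOQ (10.7), laboratory change (11.3.2), vital-sign change (11.4.2) and z scores (10.9). The HCV RNA summary uses data as observed, so the omitted subjects leave both numerator and denominator. They are not counted as failures.
- Not dependent: SVR4, SVR12 and SVR24 use the post-treatment windows of Table 4. Breakthrough is defined on consecutive measurements during treatment, and end-of-treatment failure on the end-of-treatment value (10.1). Maximum toxicity grade (11.3.2) uses post-baseline values, and the hepatic criteria use values during treatment; neither uses a visit row. The primary pharmacokinetic endpoint is steady-state AUC and does not use Table 3.

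**How many subjects?** Sixteen weeks is given outside Japan to treatment-experienced subjects with genotype 3. Under Protocol Section 5.1, treatment-experienced subjects with an indeterminate genotype, or a mixed one that includes genotype 3, default to the same duration. Neither document says how many are expected.

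**The case against.** The best defence is that the intent can be recovered. Section 6.2 says the windows map data to the time points the protocol specifies, and Week 12 is such a time point for 16-week subjects. A careful programmer would probably notice. That is fair as a reason to call this a drafting slip, but the footnote says *only*, and the SAP states that its conventions guide the programming. Correct output should not depend on someone overriding an explicit rule.

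It can also be said that the values are not wholly lost, that the affected tables are descriptive, and that they are pooled by age group and overall. All of that stands. No planned by-visit table is split by treatment duration or genotype, so the visible effect is a somewhat smaller denominator in a pooled Week 12 row. Section 10.2 plans no hypothesis test on the primary or secondary efficacy endpoints.

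A reader might infer more in two directions, and the documents support neither.

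- *That efficacy information is lost in the group where it matters most*, citing the 92.6% adult SVR12 for treatment-experienced genotype 3 as the lowest rate. A Week 12 breakthrough or ALT rise would still be counted, because those rules do not use the window. Nor is 92.6% the lowest rate in Protocol Table 3: genotype 1 adults experienced with NS5A inhibitors or protease inhibitors show 89.0%. That group is excluded from this trial, so the statement would need that qualifier.
- *That about seven children are affected*, from the adult share of 122/2256 = 5.4% and 0.054 × 125 = 6.8. The documents do not say that children share the adult mix. About 48 intensive-PK subjects must be treatment-naïve and cannot receive 16 weeks, which leaves 125 − 48 = 77, and 0.054 × 77 = 4.2. Subjects in Japan never receive 16 weeks, while the genotype defaults add some. Neither result is an estimate or a ceiling.

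**Conclusion.** Wrong as written, and minor. Taken literally, Table 3 leaves the Week 12 values of 16-week subjects without a scheduled-visit window. They count as a visit value only when they are the last on treatment. The consequence is confined to descriptive Week 12 summaries. The main efficacy, virologic failure, safety-threshold and pharmacokinetic results do not change.

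The size is one of five scheduled post-baseline treatment visits for each affected subject. The number of such subjects is not given and may be small.

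The conclusion rests on two assumptions: that the programming follows the footnote to the letter, and that the current Appendix C schedule is the one to be analysed. The SAP was written against an earlier amendment. The present list of changes shows no alteration to Appendix C note b of the Treatment Period, but the changes made by intervening amendments are not visible.

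**What to change.** In SAP Table 3, reword footnote b so that the Week 12 window applies to 12-week and 16-week treatment. Leave the corresponding footnotes of Tables 7 and 9 unchanged, because those instruments yield Week 12 data only at end of treatment. Check that the visit-assignment code follows the revised footnote.

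The cost is one footnote. No further data collection is needed, no 8-week or 12-week assignment moves, and no treatment rule is touched.

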**Safety:**

The number and percentage of subjects reporting treatment-emergent adverse events will be tabulated by Medical Dictionary for Regulatory Activities (MedDRA) system organ class and preferred term overall and by age group. Laboratory samples will be collected at Baseline, at Weeks 2, 4, 8, 12 and 16 (if applicable depending on treatment duration) and at Post-Treatment Weeks 4 through 144. Laboratory values that are potentially clinically significant, according to predefined criteria, will be identified, and the percentage of subjects with potentially clinically significant values during the Treatment Period will be summarized overall and by age group. Palatability/acceptability will be assessed for the pediatric formulation only. Additional summary statistics for safety data will be performed if deemed appropriate.

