**Post Treatment Period**

Activity	PT Wk 4	PT Wk 12	PT Wk 24	PT Wk 36	PT Wk 48	PT Wk 96	PT Wk 144	Premature D/C
Vital Signs, Weight, Height, Body Mass Index	X	X	X	X	X	X	X	X
Urine Pregnancy Test a	X							X a
Longitudinal Fibrotest and APRI		X			X	X	X	X
Hematology/Chemistry/Urinalysis b /Coagulation Panel b	X	X			X	X	X	X
HCC Assessment: Liver Ultrasound c			X			X	X	X
HCC Assessment: Alpha fetoprotein c			X		X	X	X	X
Concomitant Medication Assessment d	X	X	X	X	X	X	X	X
Adverse Event Assessment e	X	X	X	X	X	X	X	X
HCV RNA Samples	X	X	X	X	X	X	X	X
HCV Resistance Sample f	X	X	X	X	X	X	X	X
Patient Reported Outcome g		X						X g
HIV RNA Samples h	X	X						
Flow Cytometry h	X							

D/C = Discontinuation

- a. A positive urine pregnancy test requires a confirmatory serum test. (Refer to Section 5.3.1.1 [Pregnancy Test] for additional details.) Females who are experiencing menses or are nearing sexual maturation in the opinion of the PI or who are of childbearing potential should have urine pregnancy testing done through Post-Treatment Week 4. Pregnancy testing will be performed at PT Premature D/C visit only if the subject discontinues prior to PT Wk 4.
- b. Urinalysis will not be conducted after the Post-Treatment Week 4 visit. Urinalysis will be performed at PT Premature D/C visit only if the subject discontinues prior to PT Wk 4. The coagulation panel will be obtained at PTW4 for all patients. For non-cirrhotic subjects: Perform the coagulation panel at visits only if clinically indicated after post treatment Week 4.
- c. HCC assessment for subjects with compensated cirrhosis only.

- d. Concomitant medication will be collected for 30 days after study drug has been stopped, thereafter only antiviral medicines taken for the treatment of HCV and medications taken for SAEs will be recorded. See section 5.2.3.
- e. Non-serious AEs and all SAEs will be collected until 30 days post dosing. Only spontaneously reported SAEs will be collected thereafter. See Section 6.1.
- f. Resistance samples are only collected for patients that meet virologic failure criteria and should be drawn at the confirmatory visit, and if confirmed, at all subsequent visits.
- g. The PRO should be administered as the first study procedure. PRO will be accessed at the Premature D/C visit only if the subject discontinues prior to PT Wk 12.

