Note: The result closest to the scheduled time point will be used. Data must also have Study Drug End Day > 2. Vital signs and growth and development endpoints are collected at every PT visit; hematology, chemistry, urinalysis, and coagulation panels are collected at Post-Treatment Week 4 and PTDC (if subject discontinued prior to Post-Treatment Week 4). For subjects with compensated cirrhosis at baseline, chemistry and coagulation panels are collected to calculate the Child Pugh Score.

Table 6. Visit Windows for Growth Rate Calculation (Post-Treatment Period)

Scheduled Time	Nominal Day (Study Drug End Day)	Time Window (Study Drug End Days Range)
Post-Treatment Week 12	84	3 to 210
Post-Treatment Week 48	336	211 to 504
Post-Treatment Week 96	672	505 to 840
Post-Treatment Week 144	1,008	841 to 1,999
Final Post-Treatment Visit ^a	> 2 days after the last dose of study drug	

a. The last value within the Post-Treatment Period window will be used to define the final post-treatment value. The lower bound of this Final window is Study Drug End Day 3.

Note: The result closest to the scheduled time point will be used. Data must also have Study Drug End Day > 2. For the calculation of growth rate only, height will be assigned to a visit as described in the table above, then growth rate will be calculated as the change in height (millimeter) over the change in age (years) from the previous visit. If height is missing at a visit and/or the previous visit, then growth rate will be missing for the visit.

Table 7. Analysis Time Windows for PRO Instruments (Treatment Period)

Scheduled Visit	Nominal Day (Study Day)	Time Window (Study Day Range)
Day 1/Baseline ^a	1	≤ 1 ^a
Week 8 ^b	56	2 to 70
Week 12 ^c	84	71 to 98
Week 16 ^d	112	99 to 126
Final Treatment Visit ^e	2 to ≤ 2 days after last dose of study drug	

- a. Day of first dose of study drug.
- b. For 8-week treatment only.
- c. For 12-week treatment only.
- d. For 16-week treatment only.
- e. The last value within the window will be used to define the Final Treatment Visit value. The upper bound of this Final window is Study Drug End Day ≤ 2.

Note: Data must also have Study Drug End Day ≤ 2 for all windows. The result closest to the scheduled time point will be used. PRO instruments are collected at Day 1 and End of Treatment Visit, which can be at Weeks 8, 12 or 16 depending on treatment assignment.

Table 8. Analysis Time Windows for PRO Instruments (Post-Treatment Period)

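### SAP Table 5 has no scheduled-visit window for Study Drug End Days 43–70, and its note on post-treatment laboratory panels contradicts protocol Appendix C

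*SAP*

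**What the plan says.** SAP section 6.2 sets the scope of the windows: "For safety laboratory data, vital signs, and growth and development endpoints (except growth rate), the time windows specified in" Tables 3 and 5 place values at visits, Table 5 being the post-treatment one. It is titled "Laboratory Data, Vital Sign Measurements, Growth and Development Endpoints (Except Growth Rate) Visit Windows (Post-Treatment Period". Its rows give PT Week 4 (nominal Day 28) Study Drug End Days 3–42 and PT Week 12 (nominal Day 84) Days 71–126. Further rows follow for PT Weeks 24, 36, 48, 96 and 144.

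A last row, Final Post-Treatment Visit, starts at Day 3: "The last value within the Post-Treatment Period window will be used to define the final post-treatment value".

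The note under Table 5 describes collection: "hematology, chemistry, urinalysis, and coagulation panels are collected at Post-Treatment Week 4 and PTDC (if subject discontinued prior to Post-Treatment Week 4". Its next sentence adds that chemistry and coagulation are collected in cirrhotic subjects for the Child-Pugh score, without naming visits.

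The protocol synopsis says laboratory samples are taken "at Post-Treatment Weeks 4 through 144". In Appendix C, Post Treatment Period, the row beginning "Hematology/Chemistry/Urinalysis" is marked at PT Weeks 4, 12, 48, 96 and 144 and at premature discontinuation. Note b makes two exceptions. For urinalysis: "Urinalysis will not be conducted after the Post-Treatment Week 4 visit". For non-cirrhotic subjects: "Perform the coagulation panel at visits only if clinically indicated after post treatment Week 4".

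SAP 11.3.2 plans mean laboratory changes from baseline at every post-baseline visit, including whichever post-treatment visits are applicable. SAP 11.4.2 does the same for vital signs, and SAP 10.9 summarises z scores by visit.

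**The concern.** There are two separate defects. First, one clinic visit can be treated in two ways. If it falls on Days 43–70, its HCV RNA result is assigned to a visit, but the laboratory, vital-sign and z-score values from the same day are not, so they do not enter the by-visit tables.

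Second, the note describes a hematology and chemistry schedule that ends at PT Week 4, whereas the protocol continues these panels to PT Week 144. The note is the SAP's only explicit statement of when these panels are collected after treatment. A programmer deciding which post-treatment visits are applicable under 11.3.2 would have the note pointing one way and the Table 5 rows pointing the other.

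**Working it through.** **Window coverage.** The inputs are the scheduled-visit windows in the SAP's post-treatment tables. Every Study Drug End Day from 3 to 1,999 was checked against them.

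- Table 5 (laboratory, vital signs, growth except growth rate): Days 43–70 are uncovered, 70 − 43 + 1 = 28 days. No day is covered twice.
- Tables 4 (HCV RNA), 6 (growth rate), 8 (PRO) and 10 (FibroTest/APRI): no uncovered days.

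**Which visits fall in the gap.**

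- PT Week 4: 43 − 28 = 15 to 70 − 28 = 42 days late.
- PT Week 12: 84 − 70 = 14 to 84 − 43 = 41 days early.

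An on-schedule visit is unaffected. Only late, early, unscheduled or discontinuation assessments can fall here.

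**Example, a visit on Day 50.**

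| Data | Table | Assigned to |
|---|---|---|
| HCV RNA | 4 (3–56) | PT Week 4 |
| Height, for growth rate | 6 (3–210) | PT Week 12 |
| FibroTest/APRI, if drawn | 10 (3–175) | PT Week 12 |
| Laboratory, vital signs, z scores | 5 | No scheduled visit |

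On Days 57–70 the HCV RNA value would be assigned to PT Week 12 instead. It is still kept.

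**Panel schedule.** Appendix C, the Table 5 rows and the Table 5 note compare as follows for hematology and chemistry.

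| Visit | Nominal day | Appendix C | Table 5 window | In the note |
|---|---|---|---|---|
| PT Week 4 | 28 | Yes | 3–42 | Yes |
| PT Week 12 | 84 | Yes | 71–126 | No |
| PT Week 48 | 336 | Yes | 295–504 | No |
| PT Week 96 | 672 | Yes | 505–840 | No |
| PT Week 144 | 1,008 | Yes | 841–1,999 | No |
| Premature discontinuation | – | Yes, at any time | By day | Only before PT Week 4 |

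Four scheduled visits and later discontinuation visits are therefore missing from the note, although Table 5 has a window for each of the four. The note agrees with Appendix C for urinalysis. For coagulation after PT Week 4, Appendix C is routine only in cirrhotic subjects.

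The SAP also relies on later laboratory work elsewhere. Table 10 places FibroTest and APRI at PT Weeks 12, 48, 96 and 144, section 11.3.1 lists both among the chemistry variables, and the APRI formula in section 7.1 needs AST and platelets. Section 12.1, which records departures from the protocol, does not mention ending these panels at PT Week 4.

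**After the change.** The midpoint of the two nominal days is (28 + 84)/2 = 56. Splitting there gives 3–56 and 57–126, as in Table 4, and the uncovered days fall from 28 to 0.

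**The case against.** The strongest reply is that little is actually lost. The Final Post-Treatment Visit row includes Days 43–70. The maximum-toxicity-grade summary and the listing of increases to Grade 2 or higher (SAP 11.3.2) name no visit window. Confirmation of a post-nadir ALT rise uses the next consecutive measurement, not a windowed one. Growth rate, FibroTest and APRI have their own windows without gaps, and adverse events do not depend on Table 5. The note describes collection and does not restrict analysis. Finally, the SAP was written against Amendment 1 of 25 July 2017, whose schedule is not supplied, so the note may have been right when written.

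Most of this stands and limits the point to by-visit tables. Some of it is weaker than it looks. The Final Post-Treatment row uses a Day 43–70 value only if it is the child's last, and follow-up is planned to PT Week 144. Protocol 8.1.5.2 confines toxicity-grade counts to the treatment period while the SAP names no period, so that route is not assured. Vital signs and z scores have no toxicity-grade summary. Whatever the history, the note conflicts with the current protocol and with Table 5's own rows.

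A reader might also infer that the gap hides rechecks of abnormalities first seen at PT Week 4. The documents do not support this. Section 6.2 uses the assessment closest to the nominal day, so a recheck on Days 43–56 would give way to an on-time PT Week 4 value, and one on Days 57–70 to an on-time PT Week 12 value, even with the gap closed.

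**Conclusion.** Both defects hold against the current documents. Table 5 leaves 28 days in no scheduled-visit window, so a PT Week 4 visit 15 or more days late, or a PT Week 12 visit 14 or more days early, loses its laboratory, vital-sign and z-score values from the by-visit summaries while its HCV RNA value is kept. The note contradicts Appendix C for hematology and chemistry at four scheduled visits and at later premature discontinuation, which leaves the applicable visits in SAP 11.3.2 unclear.

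The effect is limited to descriptive by-visit safety and growth tables. The documents give no rate of off-schedule visits, so the number of children affected cannot be stated.

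A reader might infer that the later panels will go unanalysed and that the 144-week safety follow-up fails in its purpose. That goes too far: Table 5 has windows for all four later visits, and 11.3.2 allows them to be summarised. The note creates a contradiction, not a certain loss.

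**What to change.** In SAP Table 5, set PT Week 4 to Study Drug End Days 3–56 and PT Week 12 to Days 57–126, matching Table 4. The closest-to-nominal rule can stay as it is.

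Replace the collection statement in the note with the current Appendix C schedule: hematology and chemistry at PT Weeks 4, 12, 48, 96 and 144 and at premature discontinuation; urinalysis through PT Week 4; coagulation as in note b. State in 11.3.2 that these are the applicable post-treatment visits.

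The cost is SAP wording and the matching program settings. No visit, sample or data item is added.
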